9.4.2. Secondary Analyses

Secondary endpoints of FeNO change from baseline ratio during treatment and FEV₁ will be analysed similarly to the primary FeNO endpoint. FEV₁ will not be log-transformed.

PEF data will be listed and summarised.

Further details will be provided in the RAP.

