Primary Analyses	
FeNO, change from baseline ratio will be formally analysed following log_e-transformation. A mixed effects repeated measures model will be fitted with fixed effect terms for period, treatment, day, time, (period-level baseline)*day*time interaction term, treatment*day*time interaction term, period-level baseline and subject-level baseline. Day*time interaction term will be fitted as repeated measure. FeNO will be log_e-transformed prior to deriving subject-level baseline and period-level baseline.

Overview	Key Elements of the RAP
Secondary Analyses	FeNO change from baseline ratio during treatment and FEV1 will be analysed similarly to the primary FeNO endpoint. FEV1 will not be log-transformed prior to analysis. PEF will be summarised.
Safety Analyses	Safety data will be summarized
Biomarker Analyses	Exploratory endpoints of biomarkers will be summarized

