8.1.2. Planned Secondary Pharmacodynamic Statistical Analyses

Secondary Statistical Analyses
Endpoint

 • Change from baseline ratio of \log_e transformed FeNO during treatment with FF/VI.
Model Specification

Endpoints will be statistically analysed using a mixed models repeated measures (MMRM) model.
 
Terms fitted in the MMRM model will include: Fixed effect terms: Period, Treatment, Day, Time, Period-level baseline*Day*Time interaction term, Treatment*Day*Time interaction term, Period-level baseline and Subject-level baseline. Repeated: Day*Time interaction term.
 
Note: FeNO will be \log_e-transformed prior to deriving subject-level baseline and period-level baseline.

Model Checking & Diagnostics

 • Refer to Appendix 8: Model Checking and Diagnostics will be performed for mentioned Statistical Analyses as required.
Model Results Presentation

 • Point estimates and their associated 95% confidence intervals will be constructed for the difference [FF/VI 100/25mcg] – [Placebo] at each timepoint (AM/PM i.e. pre-dose & 12 hours) on each day. • Estimates of within-subject variability for FeNO will also be provided, where $CV_w(\%) = \text{SQRT}(\exp(\text{MSE}) - 1) \times 100$ and MSE is the residual mean squared error from the model. CV_w represents a pooled measure of within-subject variability across the regimens FF/VI 100/25mcg, Placebo and timepoints.
Endpoint

 • Change from baseline of FEV1 during treatment with FF/VI.

Secondary Statistical Analyses
Model Specification

Endpoints will be statistically analysed using a mixed models repeated measures (MMRM) model.
 
Terms fitted in the MMRM model will include:
 
Fixed effect terms: Period, Treatment, Day, Time, Period-level baseline*Day*Time interaction term, Treatment*Day*Time interaction term, Period-level baseline and Subject-level baseline.
 
 • Repeated: Day*Time interaction term.
Model Checking & Diagnostics

 • Refer to Appendix 8: Model Checking and Diagnostics will be performed for mentioned Statistical Analyses as required.
Model Results Presentation

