
 • Point estimates and their associated 95% confidence intervals will be constructed for the difference [FF/VI 100/25mcg] – [Placebo] at each timepoint (AM/PM i.e. pre-dose & 12 hours) on each day. • Estimates of within-subject variability for FEV1 will also be provided, where $CVw(\%) = \text{SQRT}(\exp(\text{MSE}) - 1) \times 100$ and MSE is the residual mean squared error from the model. CVw represents a pooled measure of within-subject variability across the regimens FF/VI 100/25mcg, Placebo and timepoints.

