11.5.2.2. Derivations and Handling of Missing Baseline Data

Definition	Reporting Details
Change from Baseline	= Post-Dose Visit Value – Baseline

NOTES :

- Unless otherwise specified, the baseline definitions specified in Section 11.5.2.1 Baseline Definitions will be used for derivations for endpoints / parameters and indicated on summaries and listings.
- Unless otherwise stated, if baseline data is missing no derivation will be performed and will be set to missing.
- The baseline definition will be footnoted on all change from baseline displays.

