
 Unscheduled visits will not be included in summary tables. Unscheduled visits will not be included in figures. All unscheduled visits will be included in listings. 	
Descriptive Summary Statistics	
Continuous Data	Refer to IDSL Statistical Principle 6.06.1
Categorical Data	N, n, frequency, %
Reporting of Pharmacodynamic Parameters	
Descriptive Summary Statistics (Log Transformed)	
N, n, geometric mean, 95% CI of geometric mean, standard deviation (SD) of logged data and [between and or within] geometric coefficient of variation (CVb/w (%)) will be reported.
 
[1] $CV_b (\%) = \sqrt{(\exp(SD^2) - 1) * 100}$ (SD = SD of log transformed data)
 
[2] $CV_w (\%) = \sqrt{(\exp(MSE) - 1) * 100}$ (MSE = mean square error from mixed effect model of loge-transformed data).

Parameters Not Being Log Transformed	FEV1
Graphical Displays	

 Refer to IDSL Statistical Principals 7.01 to 7.13. 	

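### The SAP computes the FEV1 within-subject CV with the log-scale formula, although FEV1 is analysed untransformed

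*SAP*

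**What the plan says.** **Scale of analysis.** Protocol 9.4.2 says "FEV₁ will not be log-transformed". The SAP synopsis agrees: "FEV1 will not be log-transformed prior to analysis". In SAP 11.5.3, FEV1 is the only entry in the row "Parameters Not Being Log Transformed".

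**Endpoint.** SAP 8.1.2 models "Change from baseline of FEV1 during treatment with FF/VI", and SAP 11.5.2.2 defines change from baseline as "Post-Dose Visit Value – Baseline", an arithmetic difference.

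**Variability output.** For the FEV1 model, SAP 8.1.2 continues: "Estimates of within-subject variability for FEV1 will also be provided, where". The formula it then gives takes the square root of exp(MSE) − 1 and multiplies it by 100. On the input to that formula, the SAP adds that "MSE is the residual mean squared error from the model". Apart from the parameter name, the bullet is the same as the FeNO one.

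**Definition of the formula.** SAP 11.5.3 gives the same expression among the summary statistics for log-transformed parameters, with MSE defined as the "mean square error from mixed effect model of loge-transformed data".

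**Display.** Table 2.8 (SAP 11.10.5) reports the FEV1 repeated-measures analysis using shell PD_T1, which has a %CVw column (SAP 11.11).

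**The concern.** The expression sqrt(exp(σ²) − 1) is the CV of a log-normal variable whose logarithm has variance σ². It needs a dimensionless σ², which a log-scale model supplies. The FEV1 model supplies a variance in L² or mL², and exponentiating that has no meaning as a CV. The SAP therefore applies to FEV1 a formula that its own reporting standard ties to log-transformed data.

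At stake is a planned number in a secondary-endpoint table. A reader will take %CVw as a percentage of the mean. Figures of this kind are reused: protocol 9.2.1 sizes this trial from a FeNO CVw estimated in an earlier study. A later FEV1 study planned from the tabulated value would start from the wrong variability.

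**Working it through.** **1. Check the formula where it belongs (FeNO, log scale).** Inputs from protocol 9.2.1: CVw 21.6%, N = 24, stated half-width approximately 14%.

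- σw = sqrt(ln(1 + 0.216²)) = 0.2135.
- Half-width = exp(t(0.975, 22 df) × 0.2135 × sqrt(2/24)) − 1 = 13.64%, which rounds to the stated 14%. A normal quantile in place of t gives 12.84%.
- Back-conversion: sqrt(exp(0.2135²) − 1) × 100 returns 21.6%.

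The formula is right for FeNO.

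**2. Identify the scale of the FEV1 MSE.** The response is post-dose FEV1 minus baseline, untransformed, so the residual is in litres (or mL) and the MSE is in L² (or mL²). The condition in SAP 11.5.3 is not met.

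**3. Apply the SAP formula to FEV1 in litres.** The documents give no FEV1 residual SD or mean, so both are assumptions, shown over a range. The comparison is 100 × SD / mean absolute FEV1.

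| Residual SD (L) | SAP formula | SD/mean, mean 2.5 L | SD/mean, mean 3.0 L | SD/mean, mean 3.5 L |
|---|---|---|---|---|
| 0.10 | 10.0% | 4.0% | 3.3% | 2.9% |
| 0.20 | 20.2% | 8.0% | 6.7% | 5.7% |
| 0.30 | 30.7% | 12.0% | 10.0% | 8.6% |

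Worked case: sqrt(exp(0.20²) − 1) = 0.202, against 0.20/3.0 = 0.067, a ratio of 3.03.

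The mean does not enter the SAP formula. For a small SD, sqrt(exp(SD²) − 1) is close to SD, so the output is about 100 × SD in litres. Dividing this by 100 × SD / mean leaves roughly the mean in litres. The calculated overstatement for SDs of 0.10 to 0.40 L is 2.0 to 2.1 times at a mean of 2 L, 3.0 to 3.1 times at 3 L, and 4.0 to 4.2 times at 4 L.

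**4. Change the unit to mL.** An SD of 0.20 L is 200 mL, so MSE = 200² = 40,000 and exp(40,000) overflows double precision. Even an SD of 10 mL gives 5.2 × 10²³ %. The same data thus give different results in L and mL, whereas SD/mean is identical in both.

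**The case against.** The strongest reply concerns consequence. CVw is a descriptive by-product for a secondary endpoint. The FEV1 differences and 95% intervals do not use it, the sample size rests on the FeNO CVw, no hypothesis is tested, and no re-estimation is planned. All of that stands and limits the weight of the point.

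The magnitude rests on assumed SDs and means, and the mL failure would be noticed at the first run. Both are fair. The litre result, however, would look plausible and could pass unnoticed, and the mismatch of scale does not depend on the assumed values.

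SAP 11.8.1 lets alternative models on transformed data be explored if distributional assumptions fail. That is a contingency, and the FEV1 bullet does not make the formula conditional on it.

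With the unstructured covariance matrix of SAP 11.8.1 there is one variance per day and time, not a single MSE. The variances need not be purely within-subject, because the model lists no random subject effect and the SAP does not state the subject grouping of the repeated measures. The SD/mean figures above are therefore illustrations. This gap is real, but it is separate: it affects any pooled variability figure and does not rescue the formula. The corrected line does need a pooling rule.

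Finally, PD_T1 also carries geometric-mean and ratio headings that do not suit an untransformed difference, so changing %CVw alone would not make that shell fit Table 2.8.

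**Conclusion.** The concern holds. Followed as written, the SAP puts in Table 2.8 an FEV1 %CVw that is not a coefficient of variation, ignores the mean and depends on the unit. Assuming a residual SD of 0.10 to 0.30 L and a mean of 2.5 to 3.5 L, it would show 10.0% to 30.7% where SD/mean is 2.9% to 12.0%, an overstatement of about 2.5 to 3.6 times. It would be close to a CV only if the mean happened to be near 1 in the chosen unit. The internal conflict needs no assumption; only the size does. This should be corrected before analysis, but no treatment estimate or study conclusion turns on it.

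**What to change.** In the FEV1 part of SAP 8.1.2, delete the exponential formula and report the within-subject residual SD in litres. If a CV is wanted, define CVw(%) = 100 × sqrt(within-subject variance) / overall adjusted mean of absolute FEV1. The denominator should not be the mean change, which may be near zero. The residual SD from the change model can be used directly: subject-level plus period-level baseline equals the baseline subtracted (SAP 11.5.2.1), and both are fixed effects, so modelling change or absolute FEV1 leaves the same residuals.

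State how the variance is pooled over days and times and what the subject grouping is, since the unstructured matrix yields no single MSE. Change the %CVw column of PD_T1 for Table 2.8 to match, and give that table arithmetic means and a difference in place of the geometric-mean and ratio headings. Leave the FeNO formula as it is.

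The formula correction costs one SAP line and one output column. The pooling rule and the other headings add a sentence and a shell edit. No new data and no change to the fixed effects are needed.

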9. OTHER STATISTICAL ANALYSES

9.1. Overview of Planned Biomarker Analyses

Blood Eosinophil and Serum Periostin levels will be listed and summarised if data is available. The biomarker displays will be based on the “All Subjects” population.

9.1.1. Overview of Planned Analyses

[Table 5](#) provides an overview of the planned analyses, with full details of data displays being presented in [Appendix 10](#): List of Data Displays.

Table 5 Overview of Planned Biomarker Analyses

Endpoint	Absolute				Change from Baseline			
	Summary		Individual		Summary		Individual	
	T	F	F	L	T	F	F	L
Biomarker								
Biomarker Parameters	Y		Y	Y	Y			

NOTES :

- T = Table, F = Figure, L = Listing, Y = Yes display generated.
- Summary = Represents TFL related to any summaries (descriptive statistics) of the observed raw data.

Endpoint	Absolute				Change from Baseline			
	Summary		Individual		Summary		Individual	
	T	F	F	L	T	F	F	L

- Individual = Represents FL related to any displays of individual subject observed raw data.

9.2. Overview of Safety Analyses

9.2.1. Overview of Planned Adverse Events Analyses

The safety analyses will be based on the “All Subjects” population, unless otherwise specified.

[Table 6](#) provides an overview of the planned analyses, with further details of data displays being presented in [Appendix 10](#): List of Data Displays.

Table 6 Overview of Planned Adverse Event Analyses

Endpoint	Absolute		
	Summary		Individual
	T	F	L
Adverse Events (AEs)			
All AEs by SOC and PT	Y		Y
Drug-Related AEs by SOC and PT	Y		
Subject Numbers for Individual AEs			Y
Relationship Between AE SOC, PT and Verbatim Text			Y
Serious AEs by SOC and PT			Y
AEs Leading to Withdrawal from Study / Permanent Discontinuation of Study Treatment by SOC and PT	Y		Y

NOTES:

- T = Table, F = Figures, L = Listings, Y = Yes display generated, SOC = System Organ Class, PT = Preferred Term.
- Summary = Represents TF related to any summaries (i.e. descriptive statistics) of the observed raw data.
- Individual = Represents FL related to any displays of individual subject observed raw data.

9.2.2. Overview of Planned Clinical Laboratory Analyses

The safety analyses will be based on the “All Subjects” population, unless otherwise specified.

[Table 7](#) provides an overview of the planned analyses, with further details of data displays being presented in [Appendix 10](#): List of Data Displays.

Table 7 Overview of Planned Clinical Laboratory Analyses

	Summary		Individual
	T	F	L
Lab Parameters			Y

NOTES:

- T = Table, F = Figures, L = Listings, Y = Yes display generated
- Summary = Represents TFL related to any summaries (i.e. descriptive statistics) of the observed raw data.
- Individual = Represents FL related to any displays of individual subject observed raw data.

9.2.3. Overview of Planned Other Safety Analyses

The safety analyses will be based on the “All Subjects” population, unless otherwise specified.

[Table 8](#) provides an overview of the planned analyses, with further details of data displays being presented in [Appendix 10](#): List of Data Displays.

Table 8 Overview of Planned Other Safety Analyses

	Summary		Individual
	T	F	L
Vital Signs by Visit			Y

NOTES:

- T = Table, F = Figures, L = Listings, Y = Yes display generated.
- Summary = Represents TFL related to any summaries (i.e. descriptive statistics) of the observed raw data.
- Individual = Represents FL related to any displays of individual subject observed raw data.

11. APPENDICES

Section	Appendix
RAP Section 4 : Analysis Populations	
Section 11.1	Appendix 1 : Protocol Deviation Management and Definitions for Per Protocol Population
RAP Section 5 : General Considerations for Data Analyses & Data Handling Conventions	
Section 11.2	Appendix 2 : Data Management
Section 11.3	Appendix 3 : Time and Events
Section 11.4	Appendix 4 Treatment States & Phases
Section 11.5	Appendix 5 : Data Display Standards & Handling Conventions 
 • Study Treatment & Display Descriptors • Baseline Definitions & Derivations • Reporting Process & Standards
Section 11.6	Appendix 6 : Derived and Transformed Data 
 • General, Study Population
Section 11.7	Appendix 7 : Premature Withdrawals & Handling of Missing Data 
 • Premature Withdrawals • Handling of Missing Data
Section 11.8	Appendix 8 : Model Checking and Diagnostics for Statistical Analyses
Other RAP Appendices	
Section 11.9	Appendix 9 : Abbreviations & Trade Marks
Section 11.10	Appendix 10 : List of Data Displays
Section 11.11	Appendix 11 : Example Mock Shells for Data Displays

11.1. Appendix 1: Protocol Deviation Management and Definitions for Per Protocol Population

As detailed in Section 4.1, Protocol deviations will be tracked by the study team throughout the conduct of the study in accordance with the Protocol Deviation Management Plan and a listing and summary of important Protocol Deviations will be provided. A separate listing and summary of inclusion/exclusion criteria deviations will also be produced based on the eligibility eCRF page.

A Per Protocol Population is not being defined for this study. However additional exploratory sensitivity summaries may be considered, if there are protocol deviations that may affect the primary PD endpoint analysis will be confirmed prior to unblinding. Any additional sensitivity summaries will be documented in the CSR

11.2. Appendix 2: Data Management

Data Type	Source	Format of Data	Planned Date of Final File¹	Responsibility
Study Population	Database	IDSL	DBF	CPSSO
Safety	Database	IDSL	DBF	CPSSO
Pharmacodynamic	Database	IDSL	DBF	CPSSO
Biomarker	Database	IDSL	DBF	CPSSO

1. Provided source data is clean

11.3. Appendix 3: Time & Events

Procedure	Screening (up to 42 days prior to Day 1)	Study Day (each treatment period)						Follow-up (Days 35-42) ¹²	Notes
		Day -7 (start of run-in) ¹	Day 1	Days 2-13	Days 14-19	Day 21	Day 35		
Out-patient visit to the unit	X	X	X			X	X	X	¹ Day -7 is the start of the one week run-in period and therefore this visit and the assessments on this day only apply to Treatment Period 1
Admission to the unit					X				
Informed consent	X								
Inhaler, PEF meter and FeNO device practice	X								
Inclusion and exclusion criteria/eligibility review	X	X	X						
Demography	X								
Full physical exam including height and weight	X								
Medical history (includes substance usage [and family history of premature CV disease])	X								Substances: [Drugs, Alcohol, tobacco and caffeine]
Past and current medical conditions [including cardiovascular medical history]	X								

CONFIDENTIAL

201499

Procedure	Screening (up to 42 days prior to Day 1)	Study Day (each treatment period)						Follow-up (Days 35-42) ¹²	Notes
		Day -7 (start of run-in) ¹	Day 1	Days 2-13	Days 14-19	Day 21	Day 35		
Urine pregnancy test (WCBP)	X		X ²			X		X	² Collected pre-dose
Vital signs	X								
Set up PEF and FeNO monitoring		X							
Study Treatment			X ³		X ⁴				³ Dosing every morning; dosing in the unit on Days 1 and 14 and at home on Days 2-13 ⁴ Dosing on the morning of Day 14 only
Exploratory biomarker sampling ⁵		X			X	X	X		⁵ These measurements are taken at baseline (Day -7), at the end of treatment (Day 15), on Day 21 and on Day 35.
FEV ₁ readings ⁶	X		X ⁷		X ⁸	X ⁹			⁶ Measured in the unit only ⁷ Taken pre-dose ⁸ Collected AM (pre-dose on Day 14) and PM ⁹ Collected AM only
FeNO assessment ¹⁰	X	←-----→							¹⁰ Start of collection 7 days before Day 1 (Day -7), then collected every day AM and PM through to Day 35 of each treatment period.

CONFIDENTIAL

201499

Procedure	Screening (up to 42 days prior to Day 1)	Study Day (each treatment period)						Follow-up (Days 35-42) ¹²	Notes
		Day -7 (start of run-in) ¹	Day 1	Days 2-13	Days 14-19	Day 21	Day 35		
PEF ¹¹		←=====→							¹¹ Collected AM and PM every day from Day -7 through to Day 35 for Treatment Period 1, and from Day 1 through to follow up for Treatment Period 2.
AE/SAE review		←=====→							
Concomitant medication review		←=====→							¹² Follow up visit only after Treatment period 2. The follow-up visit can be combined with the Day 35 visit for Treatment Period 2.
Issue of diary card	X					X ¹³		¹³ Second diary card given out on Day 21 of Treatment Period 1, to capture data for Treatment Period 2	

11.4. Appendix 4: Treatment States and Phases

11.4.1. Treatment States for AE Data

Treatment State	Definition
Pre-Treatment	AE Start Date < Study Treatment Start Date
On-Treatment	If AE onset date is on or after treatment start date & on or before treatment stop date. Study Treatment Start Date ≤ AE Start Date ≤ Study Treatment Stop Date [+ Lag Time]
Post-Treatment	If AE onset date is after the treatment stop date. AE Start Date > Study Treatment Stop Date
Onset Time Since 1 st Dose (Days)	If Treatment Start Date > AE Onset Date = AE Onset Date - Treatment Start Date If Treatment Start Date ≤ AE Onset Date = AE Onset Date - Treatment Start Date +1 Missing otherwise.
Duration (Days)	AE Resolution Date – AE Onset Date + 1
Drug-related	If relationship is marked 'YES' on [Inform/CRF OR value is missing].

NOTES:

- If the study treatment stop date is missing then the AE will be considered to be On-Treatment.

11.5. Appendix 5: Data Display Standards & Handling Conventions

11.5.1. Study Treatment & Sub-group Display Descriptors

Treatment Group Descriptions			
RandAll NG		Data Displays for Reporting	
Code	Description	Description	Order ^[1]
A	Placebo	Placebo	1
B	FF/VI 100/25 mcg	FF/VI 100/25 mcg	2

NOTES:

1. Order represents treatments being presented in TFL, as appropriate.

11.5.2. Baseline Definition & Derivations

11.5.2.1. Baseline Definitions

For all endpoints (except as noted in baseline definitions) the baseline value will be the latest pre-dose assessment.

Parameter	Study Assessments Considered As Baseline			Baseline Used in Data Display
	Screening	Day -7	Day 1 (Pre-Dose)	
PD				
FeNO	X	X	X	Day 1 (Pre-dose)
FEV1	X		X	Day 1 (Pre-dose)
PEF		X	X	Day 1 (Pre-dose)
Biomarker			X	Day 1 (Pre-dose)

- Note: Baseline definitions are applicable to each period

For FeNO, FEV1 analyses:

- Subject level baseline is defined as the mean of baseline across periods for each subject.
- Period level baseline is defined as the difference between the baseline and subject level baseline for each period and each subject.

11.5.2.2. Derivations and Handling of Missing Baseline Data

Definition	Reporting Details
Change from Baseline	= Post-Dose Visit Value – Baseline

NOTES :

- Unless otherwise specified, the baseline definitions specified in Section 11.5.2.1 Baseline Definitions will be used for derivations for endpoints / parameters and indicated on summaries and listings.
- Unless otherwise stated, if baseline data is missing no derivation will be performed and will be set to missing.
- The baseline definition will be footnoted on all change from baseline displays.

11.5.3. Reporting Process & Standards

Reporting Process	
Software	

 The currently supported versions of SAS software will be used. 	
Reporting Area	
HARP Server	: UK1SALX00175-HARP PROD-UK
HARP Area	: \ARPROD\ GW685698+GW642444\mid201499\Final
QC Spreadsheet	: \ARWORK\ GW685698+GW642444\mid201499\Final\Documents
Analysis Datasets	

 Analysis datasets will be created according to Legacy GSK A&R dataset standards 	
Generation of RTF Files	

 RTF files will be generated for summary displays. 	

Reporting Standards	
General	

 The current GSK Integrated Data Standards Library (IDSL) will be applied for reporting, unless otherwise stated: 
 4.03 to 4.23: General Principles 5.01 to 5.08: Principles Related to Data Listings 6.01 to 6.11: Principles Related to Summary Tables 7.01 to 7.13: Principles Related to Graphics 	
Formats	

 All data will be reported according to the actual treatment the subject received unless otherwise stated. GSK IDSL Statistical Principles (5.03 & 6.06.3) for decimal places (DP's) will be adopted for reporting of data based on the raw data collected. Numeric data will be reported at the precision collected on the eCRF. The reported precision from non eCRF sources will follow the IDSL statistical principles but may be adjusted to a clinically interpretable number of DP's. 	

Planned and Actual Time	

 Reporting for tables, figures and formal statistical analyses : 
 Planned time relative to dosing will be used in figures, summaries, statistical analyses and calculation of any derived parameters, unless otherwise stated. The impact of any major deviation from the planned assessment times and/or scheduled visit days on the analyses and interpretation of the results will be assessed as appropriate. Reporting for Data Listings: 
 Planned and actual time relative to study drug dosing will be shown in listings (Refer to IDSL Statistical Principle 5.05.1). Unscheduled or unplanned readings will be presented within the subject’s listings. Visits outside the protocol defined time-windows (i.e. recorded as protocol deviations) will be included in listings but omitted from figures, summaries and statistical analyses. 	
Unscheduled Visits	

 Unscheduled visits will not be included in summary tables. Unscheduled visits will not be included in figures. All unscheduled visits will be included in listings. 	
Descriptive Summary Statistics	
Continuous Data	Refer to IDSL Statistical Principle 6.06.1
Categorical Data	N, n, frequency, %
Reporting of Pharmacodynamic Parameters	
Descriptive Summary Statistics (Log Transformed)	
N, n, geometric mean, 95% CI of geometric mean, standard deviation (SD) of logged data and [between and or within] geometric coefficient of variation (CVb/w (%)) will be reported.
 
[1] $CV_b (\%) = \sqrt{(\exp(SD^2) - 1) * 100}$ (SD = SD of log transformed data)
 
[2] $CV_w (\%) = \sqrt{(\exp(MSE) - 1) * 100}$ (MSE = mean square error from mixed effect model of loge-transformed data).

Parameters Not Being Log Transformed	FEV1
Graphical Displays	

 Refer to IDSL Statistical Principals 7.01 to 7.13. 	

